3.1.5 Visit windows

All summaries and analyses, both efficacy and safety, which are presented by time point (e.g. “Week 52”) will use a visit window to classify the data record, which is derived from the assessment date relative to the reference start date. This approach allows appropriate classification of visits which may have occurred significantly earlier or later than the protocol assessment schedule, as well as the use of data captured at visits which have no fixed timing (notably the IPD visit), and the handling of data captured at visits for which the database label is incorrect and unresolvable.

Nominal database visit numbers will not be used in any summary or analysis by visit.

For efficacy variables, the reference start date is the date of randomisation, and relative day is therefore defined as $(Date\ of\ assessment - Date\ of\ randomisation) + 1$.

For safety variables, the reference start date is the date of first dose of IP, and relative day is therefore defined as $(Date\ of\ assessment - Date\ of\ first\ dose\ of\ IP) + 1$.

Any data collected at unscheduled or repeat visits will be listed and will be included in baseline definitions (see [Section 3.1.1](#)), and in any definitions of maximum value, minimum value or last value within the relevant study period.

Data collected at unscheduled or repeat visits will also be included in visit windows, and therefore may be included in summaries or analyses by visit or used in any sensitivity analyses which involve imputation of data from subjects with non-missing values to subjects with missing values. In the case of a missing value at a scheduled visit, which is then followed by a non-missing value at an unscheduled or repeat assessment within the same visit window, the non-missing value at the unscheduled/repeat assessment will replace the missing value at the scheduled visit.

If a subject has more than one non-missing value within the same visit window, the following rules will apply:

- The non-missing value closest to the target day will be selected for analysis at that visit
- If two non-missing values are the same distance from the target day, the earlier of the two values will be selected for analysis at that visit
- If two non-missing values are recorded on the same day and have a different assessment time associated with both of them, the value with the earliest assessment time will be selected for analysis at that visit.

- If two non-missing values (for continuous variables) are recorded on the same day and have no assessment time associated with at least one of them, or the same assessment time associated with both of them, the average of the two values will be selected for analysis at that visit. For categorical variables in this situation, the worst case will be used.
- If there are multiple ADA samples in the same visit window with both positive and negative results, the sample with a positive result and the highest titer value should be selected.

If a subject has no value within a particular visit window, then the subject will have a missing value at that visit in summaries and analysis.

The same visit window definitions below will be used regardless of whether the planned treatment period or the on-treatment period is used for analysis (see [Section 3.1.4](#)). In practice, each data record in the planned treatment period will be first identified, and then further flagged according to whether it is on-treatment or off-treatment. This flag will be used to select all eligible records for subsequent visit windowing, according to whether the derived visits are to be used in a planned treatment period or an on-treatment period analysis. It should be noted that, if treatment was discontinued within a particular visit window, the rules above for handling multiple values within the same visit window could select a different record according to whether a planned treatment period analysis or an on-treatment period analysis is needed.

Table 1 summarises the visit windows to be used for all variables unless specified otherwise. It corresponds to the full (mostly 4-weekly) protocol scheduling for clinic visits, and will be used for all variables by default, including those variables which are not captured at every clinic visit, unless it is indicated below that the visit windows in Table 2 or Table 3 should be used.

Table 1 Visit windows – all variables where not specified otherwise

Time Point	Target Day	Visit Window
Baseline (Week 0)	1	See Section 3.1.1 for baseline definitions
Week 2	15	2-21
Week 4	29	22-42
Week 8	57	43-70
Week 12	85	71-98
Week 16	113	99-126
Week 20	141	127-154

Time Point	Target Day	Visit Window
Week 24	169	155-182
Week 28	197	183-210
Week 32	225	211-238
Week 36	253	239-266
Week 40	281	267-294
Week 44	309	295-322
Week 48	337	323-350
Week 52	365	351-378
Follow-up Week 58	407	379-427
Follow-up Week 64	449	428-469

Table 2 summarises the visit windows which will be used for EQ-5D-5L, for which more frequent completion (every 2 weeks) is scheduled in the protocol.

Table 2 Visit windows – EQ-5D-5L only

Time Point	Target Day	Visit Window
Baseline (Week 0)	1	See Section 3.1.1 for baseline definitions
Week 2	15	2-21
Week 4	29	22-35
Week 6	43	36-49
Week 8	57	50-63
Week 10	71	64-77
Week 12	85	78-91
Week 14	99	92-105
Week 16	113	106-119
Week 18	127	120-133
Week 20	141	134-147
Week 22	155	148-161

Time Point	Target Day	Visit Window
Week 24	169	162-175
Week 26	183	176-189
Week 28	197	190-203
Week 30	211	204-217
Week 32	225	218-231
Week 34	239	232-245
Week 36	253	246-259
Week 38	267	260-273
Week 40	281	274-287
Week 42	295	288-301
Week 44	309	302-315
Week 46	323	316-329
Week 48	337	330-343
Week 50	351	344-357
Week 52	365	358-371

Table 3 summarises the visit windows which will be used for those variables for which the most sparse scheduling is planned in the protocol. These variables are: weight, height (adolescents only), SGRQ score, SNOT-22 score, WPAI+CIQ scores and post-BD spirometry.

Table 3 Visit windows – sparse protocol schedule

Time Point	Target Day	Visit Window
Baseline (Week 0)	1	See Section 3.1.1 for baseline definitions
Week 24 (not SNOT-22)	169	141-196
Week 28 (SNOT-22 only)	197	169-224
Week 52	365	337-392

In all cases above, no time points will be presented in summary tables or included in statistical analysis which do not correspond to the time points scheduled in the protocol for the variable in question. Listings of data will include all scheduled and unscheduled visits, including derived weekly means for data recorded beyond the final scheduled visit for all subjects randomised.

Data from the extension study (for participating subjects) will not be used for any of the visit window classifications above.

Finally, it should be noted that a visit window approach will not be used for data captured on a device daily by the subject, which will be aggregated for analysis at each relevant time point by using a weekly mean or similar approach. For this purpose, the definition of the weekly mean is provided in the relevant endpoint derivation sections of this SAP.

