- ^j For WOCBP and adolescent females, urine pregnancy test (dipstick) will only be performed at treatment visits, prior to IP administration.
- ^k All total serum IgE, IgA, IgG and IgM results will be redacted from the central laboratory reports except Visit 1, at Visit 3 prior to IP administration and any repeat testing that is performed during the screening/run-in period.
- ^l At clinic, FENO must be performed prior to spirometry assessments. All FENO measurements will be blinded for sites and subjects throughout. The sponsor will be unblinded to the FENO values prior to randomization and blinded to the FENO values post randomization.
- ^m Domiciliary FENO assessment must be performed after appropriate restrictions are met as per section 8.1.4.2 and prior to performing PEF assessment at home. All FENO measurements will be blinded for sites and subjects throughout. The sponsor will be unblinded to the FENO values prior to randomization and blinded to the FENO values post randomization.
- ⁿ Blood sample for DNA is optional and will be collected from subjects who have consented to participate in the genetic analysis component of the study.
- ^o Visit 3 spirometry must be performed on the day of randomization prior to IP administration after appropriate restriction are met as per section 8.1.2.1. For every other visit, pre-BD spirometry assessments must be performed only after appropriate restrictions are met as per section 8.1.2.1, if not this should be rescheduled to the earliest opportunity within the allowed visit window.
- ^p IP should be administered after all other assessments have been completed to a scheduled visit.

- ^q Refer to section 7.1.
- ^r The ePRO questionnaires should be completed prior to FENO and spirometry assessments at clinic.
- ^s Flow cytometry will be performed in a subset of subjects that have provided consent.
- ^t SGRQ to be completed after AQLQ(s)+12
- ^u Serum for PK must be collected, prior to IP administration.
- ^v At unscheduled visits for assessing an asthma exacerbation, the assessment/activity listed above is only the minimum needed to be performed. Other unscheduled visits may be initiated as needed, and assessments performed as per investigator's judgement.

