
Maintenance treatment with ICS and long-acting bronchodilators (including ICS/LABA combinations)
	
No changes in either dose or regimen are allowed from V1 and throughout the IP treatment and preferably 4 weeks after the last dose of IP.
 
The patients should be instructed not to take their usual asthma controller medication (i.e., LABA) prior to scheduled ECG assessment (please refer below for long-acting bronchodilator restrictions). Use of SABA should be avoided within 6 hours before ECG assessments. The medication restrictions are waived for the screening ECG at Visit 1.
 
Twice daily bronchodilators should be withheld for at least 12 hours prior to the scheduled FENO and spirometry at site.
 
Once daily bronchodilators should be withheld for at least 24 hours prior to the scheduled FENO and spirometry at site.
 
Subjects will not need a washout of their asthma medications for unscheduled visits due to asthma worsening.

Short-acting beta-agonists (SABA)
	
Regular scheduled use of SABA is not allowed from V1 and throughout the IP treatment and preferably 4 weeks after the last dose of IP, PRN use is allowed if needed, however attention should be paid to the following restrictions.
 
SABA should be withheld for at least 6 hours prior to scheduled spirometry, FENO, ECG at site with the exception of any unscheduled visits due to asthma worsening.
 
When possible, home PEF and domiciliary FENO assessments should be taken after the SABA is withheld for at least 6 hours.

Table 6 Restricted medications

Medication/class of drug:	Usage

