4.2.5 Key secondary endpoints

4.2.5.1 Main analysis

The main analysis of the key secondary endpoints (changes from baseline to Week 52 for each of pre-bronchodilator FEV₁, AQLQ(S)+12 total score, ACQ-6 score and weekly mean ASD score) will quantify the effect of the initially randomised treatment at Week 52, regardless of the treatments that subjects actually received, or whether the subjects received other controller therapy/rescue medications, including for subjects who discontinued study treatment prior to Week 52.

This analysis uses a treatment policy strategy and will therefore include all available data after treatment discontinuation until the end of the planned treatment period.

Subjects will be encouraged to continue to undergo applicable study related visits/procedures for the full 52-week period even after premature discontinuation of IP. Consequently, subjects lost to follow-up, subjects who die, subjects who withdraw their consent and subjects who choose Option 3 for their follow-up should be the only source of missing information for the key secondary analyses apart from subjects who choose Option 2 for their follow-up, who will have missing pre-BD FEV₁ following discontinuing of IP until their Week 52 visit.

Missing data will be modelled based on what was observed during the study using direct likelihood approaches, which is a valid approach under the assumption that data are missing at random (MAR).

Change from baseline for the key secondary endpoints in the tezepelumab group will be compared to that seen in the placebo group using a mixed model for repeated measures (MMRM) model. This model will be used to perform the statistical tests of the null hypotheses specified in [Section 4.1.1](#), and to estimate the treatment effect at Week 52 and its 95% confidence interval, for each endpoint.

The response variable in the model will be change from baseline at each scheduled post-randomisation visit up to and including Week 52, and irrespective of whether the subject remained on treatment and/or took other treatments. Treatment, visit, region, age (adolescents or adults) and treatment by visit interaction will be included as factors in this model. Baseline of the corresponding endpoint will also be included in the model as a continuous linear covariate. Baseline by visit interaction will not be included as a covariate in the MMRM model.

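### An FEV1 taken without bronchodilator washout at an unscheduled asthma-worsening visit can displace or fill in the scheduled pre-BD FEV1, including at Week 52; the expected effect is small but the rule should be closed.

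*SAP*

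**What the plan says.** **Where the readings come from.** In the protocol's Table 2 (Section 1.1), the unscheduled-visit column is marked for pre-BD spirometry, post-BD spirometry, clinic FENO and haematology. Footnote v adds: "At unscheduled visits for assessing an asthma exacerbation, the assessment/activity listed above is only the minimum needed to be performed".

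**Conditions of measurement.** Protocol Table 6 (Section 6.5) states: "Subjects will not need a washout of their asthma medications for unscheduled visits due to asthma worsening". The rows for SABA, LABA/LAMA, LTRA and theophylline repeat the exception. Protocol 8.1.2.1 words its withholding periods for scheduled spirometry. Footnote o of Table 2, however, asks for the restrictions to be met before pre-BD spirometry at all visits other than Visit 3, and points to 8.1.2.1.

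**How the SAP selects a value.** SAP 3.1.5 contains:
- "Nominal database visit numbers will not be used in any summary or analysis by visit".
- "Data collected at unscheduled or repeat visits will also be included in visit windows".
- "The non-missing value closest to the target day will be selected for analysis at that visit".
- A tie in distance goes to the earlier reading.
- When the scheduled value is missing, "the non-missing value at the unscheduled/repeat assessment will replace the missing value at the scheduled visit".

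**Filters.** SAP 3.2.2.1 keeps tracings graded acceptable or borderline. It has no condition on washout, visit type or exacerbation.

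**Time limit.** SAP 3.1.4 ends the planned treatment period on the date of the Week 52 visit. SAP 3.1.5 identifies records in that period first and applies the windows afterwards.

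**The concern.** The endpoint is pre-bronchodilator FEV1. At an unscheduled worsening visit the subject may have used rescue SABA or a maintenance bronchodilator shortly before the test, and the protocol permits this. The SAP then treats that reading as interchangeable with one taken under the withholding rules, and prefers it whenever it lies nearer the target day.

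For example, suppose the scheduled Week 52 spirometry is done on Day 369 after washout, and an exacerbation visit took place on Day 363 after rescue SABA. The distances from Day 365 are 4 and 2 days, so the Day 363 reading is analysed and the valid one is set aside.

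Two features make this more than noise. Substitution follows exacerbations, which the design assumes are halved on tezepelumab, so it is related to treatment arm. And FEV1 is Level 3 of the testing hierarchy, so it gates AQLQ(S)+12, ACQ-6 and the Asthma Symptom Diary score. Clinic FENO has the same withholding rules and the same exposure.

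**Working it through.** **1. The plan's own figures (SAP 1.3).** Inputs: 530 per arm, SD 400 mL, true difference 100 mL, two-sided 5%.
- Power is 98.3%, consistent with the stated 95% or higher.
- Minimum detectable difference = 1.96 × 400 × √(2/530) = 48.2 mL, consistent with the stated 50 mL.

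Neither figure depends on the windowing rule.

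**2. Days on which an unscheduled reading displaces a Week 52 value that is present.** The target is Day 365 and the window is Days 351–378 (SAP Table 1). The protocol's ±5 days corresponds to Days 360–370. Readings after the Week 52 visit fall outside the planned treatment period.
- Visit on or before Day 365: an earlier reading is further from the target, so 0 days (same-day readings aside).
- Visit *d* days after Day 365: Days 365 − *d* to 365 + *d* − 1 win, ties going to the earlier value, so 2*d* days.
- Average over Days 360–370: (2 + 4 + 6 + 8 + 10)/11 = 30/11 = 2.7 days.

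**3. Subjects affected at Week 52.** The documents give no rate of unscheduled spirometry. Assume one per exacerbation at the planning rates, 0.9 per year on placebo and 0.45 on tezepelumab (a 50% reduction), with visit days uniform over ±5.
- Placebo: 0.9 × 2.727/365.25 = 0.67%; × 530 = 3.6 subjects.
- Tezepelumab: 0.45 × 2.727/365.25 = 0.34%; × 530 = 1.8 subjects.

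**4. Effect on the Week 52 difference.** This is the between-arm difference in proportions times the average error in a displaced reading, which is also an assumption.
- 400 mL: 0.00336 × 400 = 1.3 mL.
- From −500 to +300 mL: +1.7 to −1.0 mL (tezepelumab minus placebo).
- Same range at three times the visit rate: +5.0 to −3.0 mL.

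Low readings during obstruction, more frequent on placebo, favour tezepelumab. Readings raised by a recent bronchodilator act the other way.

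**5. All eight post-baseline FEV1 visits (Weeks 2, 4, 8, 12, 16, 24, 36, 52).** At intermediate visits a reading on either side can win: 2*k* − 1 days if the visit is *k* days early, 2*k* if *k* days late.
- ±5 days, six visits: (25 + 30)/11 = 5.0 days each.
- Week 2, ±3 days: (9 + 12)/7 = 3.0 days.
- Week 52: 2.7 days.
- Total: 6 × 5.0 + 3.0 + 2.7 = 35.7 days.
- Placebo: 530 × 0.9 × 35.7/365.25 ≈ 47 values; tezepelumab ≈ 23.

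**6. Scheduled Week 52 FEV1 missing.** Any eligible unscheduled reading in the window is used: 14 earlier days if the visit was on Day 365, up to 28 if the whole window is eligible. Among such subjects this is 0.9 × 14/365.25 = 3.4% to 6.9% on placebo and 1.7% to 3.4% on tezepelumab. The documents do not say how many subjects will lack the scheduled value.

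**The case against.** **The size is negligible.** About 1.3 mL is small against an assumed effect of 100 mL and a detectable difference of 50 mL. One site spirometry per exacerbation is an assumption; some exacerbations will be managed in an emergency room or hospital. This stands: the rule does not threaten the power or the expected conclusion for FEV1.

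**Week 52 should not be treated like the other visits.** A reader might apply the 5.0-day average to Week 52 and get 6.5 against 3.3 subjects. SAP 3.1.4 and 3.1.5 do not support that, because readings after the Week 52 visit are ineligible. Nor are the 47 and 23 values a measure of bias in the confirmatory test. That test concerns Week 52, and earlier displaced values have little influence when Week 52 is observed.

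**Treatment policy covers worsening.** A reader might infer that any reading taken during an exacerbation is an error. SAP 4.2.5.1 uses a treatment policy strategy, and a scheduled visit that happens to fall in an exacerbation counts. The defect is the missing washout, not the clinical state.

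**The scheduled-visit wording is no clear contradiction.** SAP 4.2.5.1 says "The response variable in the model will be change from baseline at each scheduled" post-randomisation visit, which can be read as referring to the windowed time points.

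**Footnote o may already require washout.** It can be read as covering unscheduled visits. But it refers to rules worded for scheduled spirometry and to rescheduling within a visit window that unscheduled visits do not have, while Table 6 expressly waives washout. Even on the strict reading, the SAP does not check compliance.

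**Windowing unscheduled data is routine.** That is reasonable for repeats under the same conditions. Here the conditions differ by protocol. The SAP does filter on validity elsewhere: SAP 4.2.9.1 restricts the PK summaries by time since the previous dose.

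**Conclusion.** The gap is real and follows from the text: the plan can analyse a reading that is not pre-bronchodilator as pre-BD FEV1, at Week 52 and at earlier visits, in place of a valid reading or to fill a missing one. It is a defect of endpoint definition with a small expected effect, about 3.6 against 1.8 subjects and about 1.3 mL at Week 52 where the scheduled value is present. Those figures rest on unscheduled spirometry at the planned exacerbation rates, visit days uniform over ±5, and a 400 mL error; the documents supply none of these three. The direction is uncertain, and substitution for missing scheduled values comes on top.

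A reader might extend the point to eosinophils because the same windowing rule applies to them. The documents do not support that, since eosinophil counts have no bronchodilator withholding rule. The point covers pre-BD spirometry and clinic FENO. It is worth correcting because it is related to arm, touches a gatekeeping endpoint and is cheap to remove.

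**What to change.** In SAP 3.1.5 and 3.2.2.1, for pre-BD spirometry and clinic FENO:

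- Within a window, a scheduled, rescheduled or repeat value obtained under the withholding rules takes precedence, whatever its distance from the target day relative to a reading without washout.
- A reading from an unscheduled worsening visit without documented washout is not eligible for the main analysis and is listed.
- A sensitivity analysis includes such a reading where it is the only value in the window.
- Repeat tests that meet the withholding rules stay eligible. Eosinophils are unchanged.

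The protocol should also reconcile footnote o of Table 2 with the Table 6 waiver, so that it is clear which conditions apply to spirometry at unscheduled visits.

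The cost is a few sentences in the SAP, a filter on visit type and washout in the programming, and one sensitivity analysis. The design figures do not change. The downside is that a few subjects whose only value in the window was taken without washout become missing and are handled under MAR in the main analysis. These subjects are exacerbating and more often on placebo, so the missingness may be informative; the sensitivity analysis is there to show whether it matters.

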The study will consist of a screening/run in period between 5-6 weeks, a planned treatment period of 52 weeks and a post-treatment follow-up period of 12 weeks. The follow-up period may not apply to subjects who participate in the extension study. Any data collected after a subject is enrolled in the extension study will not be included in the analyses described in this SAP.

During the planned treatment period, investigational product (IP) will be administered Q4W starting at the randomisation visit (Week 0; Day 1), with the last administration occurring at Week 48. IP will not be administered at Week 52. Subjects who prematurely discontinue IP will be encouraged to remain in the study and undergo appropriate study visits/procedures for the full planned 52-week treatment period, despite no longer receiving treatment. At the IP Discontinuation (IPD) visit, the subject will be given the following 3 options (further details are given in the CSP Section 7.1.1):

1. The subject should be encouraged to return for all regular clinic visits and perform all scheduled assessments until he/she completes a total of 52 weeks in the study (the planned treatment period)
2. The subject will be offered follow-up on a monthly basis via telephone calls while continuing eDiary and PEF completion (no further procedures will be performed), until the subject completes 52 weeks in the study
3. If the subject cannot or does not wish to comply with either of the options above (or any component of them, such as only telephone-based visits without completion of the eDiary and PEF), then the investigator will only contact the subject at 52 weeks post-randomisation. No study assessments will be performed prior to this contact.

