2.1.5 Definition of on-treatment

Efficacy analyses

Any efficacy assessment date which occurs between the date of randomisation and minimum (date of last dose of IP + 33 days, date of death, date of study withdrawal) will be considered on-treatment. In particular, this allows a subject who completes treatment according to the protocol to have their Week 52 data included as on-treatment, provided Week 52 is within the protocol visit window after the last dose of IP at Week 48.

Safety analyses

Safety analyses will be presented for subjects in the safety analysis set, which is described further in [Section 2.1.2](#).

For this purpose, any adverse event start date, or any safety assessment date (e.g. laboratory, vital signs), which occurs between the date of first dose of IP and minimum (date of last dose of IP + 33 days, date of death, date of study withdrawal) will be considered on-treatment. In particular, this allows inclusion of any safety-related information which may be reported at or generated from the IPD visit to be considered as on-treatment, provided the IPD visit is within the protocol visit window after premature discontinuation of IP.

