4.2.5.3 Supplementary analyses

The MAR analyses specified in [Section 4.2.5.1](#) will be repeated using on-treatment data only, where the definition of on-treatment is given in [Section 2.1.5](#).

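### Do the SAP's visit windows waste pre-BD FEV1 and AQLQ(S)+12 values taken at the IP-discontinuation visit?

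*SAP*

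**What the plan says.** SAP 3.1.5 replaces nominal visit labels with date windows. One stated reason is to allow "the use of data captured at visits which have no fixed timing (notably the IPD visit"). SAP Table 1, with mostly 4-week windows, "will be used for all variables by default, including those variables which are not captured at every clinic visit", unless Table 2 (EQ-5D-5L) or Table 3 (a named list of sparsely measured variables) applies. Neither pre-BD FEV1 nor AQLQ(S)+12 is on those two lists. The section then rules out summarising any time point, or having it "included in statistical analysis which do not correspond to the time points scheduled in the protocol for the variable in question".

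The same windows serve both analysis periods: "The same visit window definitions below will be used regardless of whether the planned treatment period or the on-treatment period is used for analysis". SAP 4.2.5.3 says the key secondary analyses "will be repeated using on-treatment data only". SAP 2.1.5 sets that period: "Any efficacy assessment date which occurs between the date of randomisation and minimum (date of last dose of IP + 33 days", or death or withdrawal if earlier).

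Protocol Table 2 schedules pre-BD FEV1 at Weeks 2, 4, 8, 12, 16, 24, 36 and 52, and AQLQ(S)+12 at Weeks 4, 12, 24, 36 and 52. Both are also measured at the IPD visit, which Protocol 7.1.1 places 4 weeks (±5 days) after the last dose.

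**The concern.** The windowing section appears to work against its own aim. The protocol asks a subject who stops IP to attend for spirometry and a questionnaire. The SAP says date windows are there so that such data can be used, and then leaves many of the values unmodelled because they fall in weeks not scheduled for that variable. ACQ-6, which is measured at every visit, loses none.

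The on-treatment supplementary analysis is where this would be felt. An IPD visit held on time counts as on-treatment and the next scheduled visit does not, so the IPD value is the discontinuer's last scheduled on-treatment measurement. If lung function was falling as the subject stopped, that value carries information on the fall. At stake would be some precision and some of the credibility of the missing-at-random assumption, for two key secondary endpoints. The primary endpoint is not involved.

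**Working it through.** The plan gives no figure of its own here, so the check is an enumeration followed by a precision calculation.

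**Inputs.** Doses are given every 4 weeks from Week 0 to Week 48, so a premature last dose falls at Week 0, 4, …, 44 (12 cases). Target day = 7 × week + 1. IPD day = last-dose day + 28. The on-treatment limit is last-dose day + 33. Scheduled values are taken as present up to the last dose.

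**Which IPD values are modelled.** The gap is the number of days from the last value used to the IPD value.

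| Last dose (week) | IPD (week) | FEV1 gap | AQLQ(S)+12 gap |
|---|---|---|---|
| 0 | 4 | 0 | 0 |
| 4 | 8 | 0 | 28 |
| 8 | 12 | 0 | 0 |
| 12 | 16 | 0 | 28 |
| 16 | 20 | 28 | 56 |
| 20 | 24 | 0 | 0 |
| 24 | 28 | 28 | 28 |
| 28 | 32 | 56 | 56 |
| 32 | 36 | 0 | 0 |
| 36 | 40 | 28 | 28 |
| 40 | 44 | 56 | 56 |
| 44 | 48 | 84 | 84 |

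A gap above 0 means the IPD value is not modelled. That is 6 of 12 for FEV1 (sum 280 days, mean 280/12 = 23.3) and 8 of 12 for AQLQ(S)+12 (sum 364, mean 30.3).

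**Visit tolerance.** With ±5 days on the dose visit and ±5 on the IPD visit, every IPD date stays in its nominal Table 1 window, so the counts hold. The IPD visit falls 23 to 33 days after the last dose, within the limit. The next scheduled visit is at least 56 − 5 − 5 = 46 days after it, so it is off-treatment.

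**What wider windows would recover.** Join the unscheduled windows to scheduled ones: Week 24 = Days 127–210 and Week 36 = Days 211–294, plus Week 12 = Days 43–126 for AQLQ(S)+12. Keep the closest-to-target rule. IPD values at Weeks 20 and 32 then enter for FEV1, and at Weeks 8, 20 and 32 for AQLQ(S)+12. The others lose to a closer scheduled value (Weeks 28 and 40, and Week 16 for AQLQ(S)+12) or remain outside any scheduled window (Weeks 44 and 48). The mean gap falls to 196/12 = 16.3 days for FEV1 and 224/12 = 18.7 for AQLQ(S)+12. The 84-day maximum does not move.

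**Number of values.** The documents give no rate or timing of IP discontinuation. Assume 10% of 1060, spread evenly over the 12 times, all attending:
- FEV1: 1060 × 0.10 × 2/12 = 17.7 values, out of 8 × 1060 = 8480 planned (0.2%).
- AQLQ(S)+12: 1060 × 0.10 × 3/12 = 26.5 values, out of 5 × 1060 = 5300 planned (0.5%).

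**Effect on the Week 52 estimate.** For one arm, sum the information matrix n_k R_k⁻¹ over missingness patterns k, where R_k is the correlation matrix of the visits observed in that pattern. Invert the sum, and take the square root of twice the Week 52 diagonal element. I compared the on-treatment analysis under current and joined windows. Assumptions: 530 per arm; 5%, 10% or 15% discontinuing evenly; compound-symmetric or autoregressive correlation (per 4 weeks) of 0.5 to 0.9; recovered values treated as taken exactly on target, which favours the wider windows. The standard error falls by 0.001% to 0.18% for FEV1 and by 0.001% to 0.23% for AQLQ(S)+12. With the planning SD of 400 mL, the complete-data standard error is 400 × √(2/530) = 24.6 mL, so the largest FEV1 gain is about 24.6 × 0.0018 = 0.04 mL.

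**A rough bound on bias.** Suppose every unmodelled IPD value in one arm lay a full planned effect (100 mL, or 0.3 units) from what the model predicts, none did so in the other arm, and the whole difference persisted to Week 52. With 10% discontinuing, the on-treatment estimate moves by 0.10 × 6/12 × 100 = 5 mL for FEV1 and by 0.10 × 8/12 × 0.3 = 0.02 units for AQLQ(S)+12. At 15% the figures are 7.5 mL and 0.03. The plan's minimum detectable differences are 50 mL and 0.16.

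**The case for a change.** The best case for a change is that SAP 3.1.5 names the IPD visit as a reason for windowing and then leaves half or more of its nominal times unused for two key secondary endpoints. Table 3 can even admit post-BD spirometry from an IPD visit whose pre-BD FEV1 goes unused. The IPD column in Protocol Table 2 does not rescue the text, because Table 1 has no IPD time point and nominal visit numbers are not used. The counts and the tension in the wording both stand.

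The rest is weaker:

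- The SAP says windowing allows the use of IPD data; it does not promise that every value is used. SAP 4.2.5.1 defines the response at scheduled visits, so the two sections agree.
- Days since the last value used would measure harm under last-value-carried-forward. In a mixed model under missing-at-random the last value has no such role.
- The post-BD contrast, at IPD Weeks 20 and 48, is a knife-edge. Days 141 and 337 are exactly the lower bounds in Table 3, and with ±5 days on both visits the value is admitted in 66 of 121 combinations.
- In the main analysis, subjects on full follow-up contribute later scheduled values. What is lost there concerns subjects who withdraw after the IPD visit or choose Option 3, and FEV1 under Option 2.

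A side point concerns the follow-up visit 16 weeks after the last dose. SAP 4.2.5.1 describes Option 2 FEV1 as missing "following discontinuing of IP until their Week 52 visit", and SAP 1.2 says of Option 3: "No study assessments will be performed prior to this contact". Protocol 7.1.1 sends both groups to that visit with reference to Visit 19, where Protocol Table 2 lists pre-BD spirometry, although it also says no further procedures are done under Option 2. These passages should be reconciled. The SAP sentences are descriptive, though: any FEV1 recorded then would be windowed by date like any other, so no analysis rule depends on the answer.

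**Conclusion.** No change is needed. The rule leaves IPD values unmodelled at 6 of 12 nominal times for pre-BD FEV1 and 8 of 12 for AQLQ(S)+12. These are shares of visit times, not of subjects. No Week 52-window value is lost, no bias is shown, and the values are still listed.

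The wider windows that would recover some of them gain at most about 0.2% in the on-treatment Week 52 standard error, under the assumed discontinuation rates and correlations. They also carry costs. Windows would reach 42 days from target, against 28 for the widest in Table 3, and the recovered values would sit 18 to 38 days early. The main and on-treatment analyses would no longer share windows, so a difference between them could reflect windowing. Keeping unscheduled worsening-visit FEV1, for which washout is waived, out of the joined windows would discard values that SAP 3.1.5 now lets stand in for a missing scheduled one.

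The conclusion rests on IPD visits held within ±5 days and discontinuation spread roughly evenly. Heavy clustering of last doses at Weeks 16 and 28 (and Week 4 for AQLQ(S)+12) would raise the gain, but for a supplementary analysis only. A sentence saying that IPD values in unscheduled windows are listed only would help readers; the analysis does not depend on it.
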